12.4 Vital Signs

Vital signs include systolic blood pressure, diastolic blood pressure, pulse rate, respiratory rate, oral temperature (°C)

The result, change from baseline and % change from baseline for all vital sign parameters will be listed and summarized descriptively by scheduled visit.

12.5 BMI and Z-scores

Weight, height and BMI will be recorded throughout the study.

The result, change from baseline and % change from baseline for weight, height and BMI will be listed and summarized descriptively by scheduled visit. Descriptive statistics will also be presented for the following age groups: 2 to ≤5 years, > 5 to < 8 years and ≥8 years.

The BMI percentiles and Z-scores are designed to take into account the amount of weight gain that would be expected due to normal growth in children and adolescents. The BMI percentiles and Z-scores are categorized by age and gender standardized values (corresponding to a normal distribution with mean 0 and a SD of 1) of the actual weight measurements, based on the Growth Charts provided by the Centers for Disease Control (CDC).

A SAS program and reference data can be downloaded from the following webpage:

<http://www.cdc.gov/nccdphp/dnpao/growthcharts/resources/sas.htm>. (Appendix B)

The program will calculate the percentiles and z-scores (standard deviations) for a child's sex and age for BMI, weight, height, and head circumference based on the CDC growth charts. The reference data contains the L, M, and S parameters needed to generate the percentiles and z-scores.

An input file should be setup containing AGEMOS (age in months), SEX (coded as 1 for boys and 2 for girls) and BMI. An output file will be generated containing BMIPCT (BMI percentile) and BMIZ (BMI Z-Score).

The BMI percentiles will be used to categorize the subject's weight as follows:

Weight Status Category	Percentile Range
Underweight	Less than the 5th percentile
Normal or Healthy Weight	5th percentile to less than the 85th percentile
Overweight	85th to less than the 95th percentile
Obese	Equal to or greater than the 95th percentile

A shift table will be presented for the change in weight status category from baseline to end of double-blind treatment, to the end of the first open-label phase and to the end of study.

The Z-score and change from baseline will be listed and summarized descriptively by scheduled visit.

BMI and Z-score after 3 weeks and 13 weeks of double blind treatment and during open-label treatment will be analysed as for TST.

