- To assess the treatment effect of Circadin® 2/5/10 mg on pubertal status using the Tanner scale in children ≥ 8 years of age. For children ≤ 5 years of age, only height and head circumference will be used to stage children development. Between the age of 5 and 8 the children's physical development will be determined using the BMI (baseline through Week 108)
- In children diagnosed with epilepsy, to compare the effect of Circadin® 2/5 mg to that of placebo on the number and severity of epilepsy seizures during double-blind treatment and to assess the effect of Circadin® 2/5/10 mg during the open-label period using seizure diaries

4 Endpoints

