11.3 Exploratory Efficacy Variables

11.3.1 Sleep and Nap Diary by Visit

The change from baseline at 3 weeks of double-blind treatment is analysed in the same model as the change from baseline at 13 weeks. From that model, the adjusted mean change from baseline (and standard error) in TST after 3 weeks of treatment for each treatment group will be calculated and the associated 95% CI for the change presented. Furthermore, the estimated difference (and standard error) between treatments will be estimated, the associated 95% confidence interval presented and the null hypothesis that these means are equal will be tested.

For the TST during open-label treatment the estimated change from baseline (and standard error) will be calculated and associated 95% CI for the change will be presented for each visit. A paired t-test will be performed comparing the mean TST at visit to the baseline mean.

Example SAS code for this analysis is given below:

```
proc means data=tst mean stderr lclm uclm probt;  
  var chg;  
run;
```

These analyses will be repeated for the other sleep variables derived from the Sleep and Nap diary.

A subject is defined as a TST responder if the mean change from baseline in TST is 45 minutes or greater (increase in TST) over the 14 days prior to each scheduled visit. A subject is defined as a sleep latency responder if the mean change from baseline in sleep latency is 15 minutes or greater (reduction in SL) over the 14 days prior to each scheduled visit. Frequency tables of TST response and sleep latency response will be presented by scheduled visit.

For Visits 3 and 4, the TST response rate and sleep latency response rate will be analysed using logistic regression. Subjects without a mean TST (or mean sleep latency) at a visit will be taken to be non-responders in this analysis. The model will include terms for treatment and mean baseline value of TST and sleep latency respectively. From the model the estimated odds of responding will be calculated, as will estimated odds ratios, associated 95% CI and p-values for testing the null hypothesis of the odds ratio being 1.

Example SAS code for this analysis is given below:

```
proc genmod data=resp;  
  class trtp;  
  model resp=trtp base/link=logit dist=bin;  
  lsmeans trtp/diff cl om exp;  
run;
```

The responder analysis will be repeated on all non-missing data. That is, subjects without a mean TST (or mean sleep latency) at a visit will not be included in the analysis.

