Table 14.3.2.7	Serious Adverse Events by System Organ Class and Preferred Term: Open Label Phase	Safety Set
Table 14.3.2.8	Treatment Related Adverse Events by System Organ Class and Preferred Term: Double Blind Phase	Safety Set
Table 14.3.2.9	Treatment Related Adverse Events by System Organ Class and Preferred Term: Open Label Phase	Safety Set
Table 14.3.2.10	Treatment Emergent Adverse Events by System Organ Class, Preferred Term and Severity: Double Blind Phase	Safety Set
Table 14.3.2.11	Treatment Emergent Adverse Events by System Organ Class, Preferred Term and Severity: Open Label Phase	Safety Set
Table 14.3.2.12	Treatment Emergent Adverse Events Leading to Study Drug Discontinuation by System Organ Class and Preferred Term: Double Blind Phase	Safety Set
Table 14.3.2.13	Treatment Emergent Adverse Events Leading to Study Drug Discontinuation by System Organ Class and Preferred Term: Open Label Phase	Safety Set
Table 14.3.2.14	Treatment Emergent Adverse Events on Active Treatment by System Organ Class and Preferred Term: Cumulative	Safety Set
Table 14.3.2.15	Serious Adverse Events on Active Treatment by System Organ Class and Preferred Term: Cumulative	Safety Set
Table 14.3.2.16	Treatment Emergent Adverse Events Study Drug Discontinuation on Active Treatment by System Organ Class and Preferred Term: Cumulative	Safety Set
Table 14.3.3	Vital Sign Parameters and Change from Baseline – Descriptive Statistics	Safety Set
Table 14.3.4.1	Weight and Change from Baseline – Descriptive Statistics	Safety Set
Table 14.3.4.2	Weight and Change from Baseline by Age Group – Descriptive Statistics	Safety Set
Table 14.3.4.3	Height and Change from Baseline – Descriptive Statistics	Safety Set
Table 14.3.4.4	Height and Change from Baseline by Age Group – Descriptive Statistics	Safety Set
Table 14.3.5.1	BMI and Change from Baseline – Descriptive Statistics	Safety Set
Table 14.3.5.2	BMI and Change from Baseline by Age Group – Descriptive Statistics	Safety Set
Table 14.3.5.3	Shift Table of Change in BMI Weight Status	Safety Set

Table Number	Table Title	Population
Table 14.3.5.4	BMI Change from Baseline at 3 Weeks Double Blind – MMRM Analysis	FAS Set
Table 14.3.5.5	BMI Change from Baseline at 13 Weeks Double Blind – MMRM Analysis	FAS Set
Table 14.3.5.6	BMI Change from Baseline Analysis During the Open Label Phase and Run-Out Period	FAS Set
Table 14.3.5.7	BMI Z-Score and Change from Baseline – Descriptive Statistics	Safety Set

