proc sort data=_cinht; by sex _htcat;
data crefht; set reffdir.CDCref_d
    (keep=denom sex _ht1 _ht2 _lwht1 _lwht2 _mwht1 _mwht2 _swht1 _swht2);
    where denom='height'; _htcat=_ht1; length sex 3;
    proc sort data=crefht; by sex _htcat;

data finfht; merge _cinht (in=a) crefht; by sex _htcat;
    if a & (77 < height <122);
    htint = _ht2- _ht1; dht=height - _ht1;
array l _lwh _mwh _swh;
array l1 _lwht1 _mwht1 _swht1;
array l2 _lwht2 _mwht2 _swht2;
do over l; l = l1 + (dht * (l2 - l1)) / htint; end;

%_zscore(weight, _lwh, _mwh, _swh, wstz, wstpct, _Fwstz);
    %_cuts(_Fwstz, _bivwst, -4, 5);
keep _id sex _agecat agemos weight _Fwstz _bivwst wstz wstpct;

*** combine the for-age, for-length, and for-height calcs;
proc sort data=finflg; by _id; proc sort data=finfht; by _id;
data lenht; merge finflg finfht; by _id;

proc sort data=finfage; by _id;
data _outdata; **define height vars as max of standing height and lenth vars;
    merge finfage lenht; by _id;

    array a stz stpct _bivst _fstatz wstz wstpct _bivwst _fwstz ;
    array b lgz lgpct _bivlg _flenz wlz wlpct _bivwlg _fwlz;
    array c haz hapct _bivht _Fhaz whz whpct _bivwh _Fwhz;
    do over c; if agemos ge 24 then c=a; else c=b; end;
    /* do over c; c=max(a,b); */
```

```

    if .z < weight< 0.01 then do; waz=.; wapct=.; bmiz=.; bmipct=.; whz=.;
whpct=.; end;
    if .z < height< 0.01 then do; haz=.; hapct=.; bmiz=.; bmipct=.; whz=.;
whpct=.; end;
    if .z < headcir< 0.01 then do; headcz=.; headcpct=.; end;

    min= min(of _bivht _bivwt _bivbmi _bivac _bivhc _bivssf _bivtsf _bivwh);
        if min>=0 then _bivlow=0; else if min= -1 then _bivlow=1;
    max= max(of _bivht _bivwt _bivbmi _bivac _bivhc _bivssf _bivtsf _bivwh);
        if max=0 or max= -1 then _bivhigh=0; else if max= 1 then
_bivhigh=1;

data _outdata; set _outdata;
keep _Fbmiz _Fhaz _Fheadcz _Flenz _Fstatz _Fwaz _Fwhz _fwstz _Fwlz _bivbmi
_bivhc
    _bivhigh _bivht _bivlg _bivlow _bivst _bivwh _bivwlg _bivwst _bivwt
agemos bmi bmipct
    bmipct95 bmiz height haz stz lgz headcir headcpct headcz _id lgpct sex
stpct wapct
    waz whpct whz hapct wstz wstpct _fstatz;

data _outdata; set _outdata _old; ** combine with older, excluded people;
    label waz='weight-for-age Z'  wapct='weight-for-age percentile'
_fwaz='modified weight-for-age Z'
        _bivwt='BIV weight-for-age'
    haz='height-for-age Z'  hapct='height-for-age percentile'
_bivht='BIV height-for-age'
        _fhaz='modified height-for-age Z'

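### Height, weight and head circumference are summarised only as raw change, so 91 open-label weeks without a control cannot show altered growth, least of all in children aged 5 or under

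*SAP*

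**What the plan says.** SAP 12.5 covers weight, height and BMI: "The result, change from baseline and % change from baseline for weight, height and BMI will be listed and summarized descriptively by scheduled visit". The same statistics are repeated for three age bands (2 to 5, over 5 to under 8, and 8 or more years). SAP 12.6 uses the same raw format for head circumference. The outputs are Tables 14.3.4.1 to 14.3.4.4 (weight and height) and 14.3.7.1 to 14.3.7.2 (head circumference).

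BMI receives more. SAP 12.5 adds BMI percentiles and a BMI Z-score, explains that these exist to allow for expected growth, and plans: "The Z-score and change from baseline will be listed and summarized descriptively by scheduled visit". The table list shows that this refers to the BMI Z-score only (Table 14.3.5.7). The section also says "A shift table will be presented for the change in weight status category from baseline to end of double-blind treatment", with the shift table continuing to end of study, and "BMI and Z-score after 3 weeks and 13 weeks of double blind treatment and during open-label treatment will be analysed as for TST". For the open-label phase, SAP 11.3.1 defines the TST method: "A paired t-test will be performed comparing the mean TST at visit to the baseline mean".

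The exploratory objective (SAP 3.3) is physical development from baseline through Week 108. For children aged 5 or under, "only height and head circumference will be used to stage children development".

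SAP 12.5 notes that the cited program can produce Z-scores for BMI, weight, height and head circumference. The input file it specifies holds only age in months, sex and BMI, and the specified output is the BMI percentile and BMI Z-score.

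**The concern.** A growing child gets taller and heavier with or without the drug. A raw change therefore carries information about treatment only when a concurrent control shows the expected change. After Week 15 there is none. A table showing that mean height rose by some number of centimetres by Week 106 is compatible with normal, slowed or accelerated growth, and % change from baseline does not cure this.

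At stake is the development objective in the youngest children. Their two designated measures are the ones left unstandardised. The BMI Z-score does not fill the gap, because it does not measure linear growth or head growth.

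**Working it through.** **1. Length of follow-up without a control.** Inputs are from SAP 5 and 4.3: open-label periods of 13 and 78 weeks, with Week 106 stated as 91 weeks of open-label treatment.
- 13 + 78 = 91 weeks, and 106 − 15 = 91 weeks. The stated figure reproduces.
- 91 / 52.18 = 1.74 years.
- Baseline (Week 2) to Week 106 is 104 weeks, or 1.99 years; the first 13 of those weeks are placebo-controlled. A further 2 weeks of placebo run-out end at Week 108.

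**2. Development measures by age band (SAP 12.5, 12.6 and 16.1).**

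| Age band | Designated measure | Age-referenced form planned? |
|---|---|---|
| 8 years or more | Tanner stage | Yes: SD score (14.3.6.4 to 14.3.6.6) |
| Between 5 and 8 | BMI | Yes: BMI Z-score (14.3.5.7 to 14.3.5.10) and percentile shift table (14.3.5.3) |
| 5 years or less | Height, head circumference | No: raw values only (14.3.4.3, 14.3.4.4, 14.3.7.1, 14.3.7.2) |

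Only the youngest band has no standardised version of its own measures.

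**3. What raw height shows.** Assumption, not in the documents: median growth of 4 to 8 cm/year and a starting height of 100 to 140 cm. For a child exactly on the median throughout:
- Week 2 to Week 106: 4 × 1.99 = 8.0 cm up to 8 × 1.99 = 15.9 cm, which is 5.7% (8.0/140) to 15.9% (15.9/100).
- Open-label phase only: 4 × 1.74 = 7.0 cm up to 8 × 1.74 = 14.0 cm.
- Change in height Z-score: 0 in every case, because observed height equals the reference median at both ages.

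A true slowing of 0.5 cm/year (assumed) over the open-label phase would be 0.5 × 1.74 = 0.87 cm. To recognise it in a raw mean, the reader must know the gain expected for that mix of ages and sexes, and the tables do not supply it. The 7 to 14 cm range is a range of assumed mean growth, not a sampling SD, so this is not a power statement.

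**4. What the program returns.** Appendix B contains the calculations for height, weight and head-circumference Z-scores, and its retained variables include "bmipct95 bmiz height haz stz lgz headcir headcpct headcz _id lgpct sex". Each Z-score is calculated only when its measurement is present. Running that logic with only the inputs SAP 12.5 specifies gives a BMI Z-score, with height and weight Z-scores missing. With a height supplied, the height Z-score is returned.

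**5. Raw BMI in the open-label phase.** SAP 12.5 with SAP 11.3.1 gives a paired t-test on raw BMI, reported as "BMI Change from Baseline Analysis During the Open Label Phase and Run-Out Period" (Table 14.3.5.6). As an illustration, take n = 50 (the minimum expected completers), an assumed SD of change of 1.5 kg/m² and no drug effect. From the non-central t distribution, an age-related drift of 0.3, 0.5 or 1.0 kg/m² is declared significant with probability 28%, 64% or 99.6%. At a drift of 0.5, an SD of 1.0 gives 93% and an SD of 2.0 gives 41%. Drift and SD are both assumptions.

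**The case against.** The strongest case for the plan has five parts.

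- **The SAP follows the protocol.** Protocol 12.8.3 itself asks for descriptive statistics on height and head circumference in children aged 5 or under. That is true, but adding a standardised column remains descriptive and departs from nothing.
- **The raw tables carry no test.** A reader might infer that the plan treats normal growth as a treatment change. The documents do not support that: height, weight and head circumference are summarised without inference, and no section interprets them so. The harm is that the tables are uninformative, not that they assert a false effect.
- **BMI is covered.** A reader might also infer that BMI is judged on raw values. It is not: the BMI Z-score and the percentile-based shift table run to end of study. The raw BMI test serves a stated objective, since SAP 3.3 names both BMI and Z-score against baseline, and Table 14.3.5.10 gives the Z-score counterpart. Deleting Table 14.3.5.6 is therefore not warranted.
- **There is some control and some stratification.** Double-blind tables are by arm, and the raw tables are split by age. But 13 weeks is short for growth, and a band spanning ages 2 to 5 with both sexes still has no stated expected gain.
- **The data can be standardised later.** The endpoints are exploratory, and age, sex and the measurements are all collected. This limits the severity, but specifying the summary now costs almost nothing and avoids a post hoc choice.

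**Conclusion.** The point holds in a limited form. Height, weight and head circumference have no planned standardised summary. Over 91 open-label weeks (1.74 years) without a concurrent control, raw change cannot separate normal from altered growth. Children aged 5 or under are the most affected, because no age-referenced form of their own development measures is planned.

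This conclusion rests on the design and the table list; the growth rates are assumptions that only illustrate scale. The raw BMI rejection rates also depend on assumed drift and SD, and support no more than a sentence saying which BMI analysis governs interpretation.

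Two stronger readings fail. The uncontrolled open-label period is not two full years. Nor are the missing Z-scores already produced and merely left out of the tables: the code can compute them, but not from the input file as specified. No primary or secondary efficacy conclusion is affected. The change is worth making because it lets the trial address its own development objective.

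**What to change.** - **Input file (SAP 12.5):** add weight, height and head circumference to age, sex and BMI, and list the height-for-age (haz), weight-for-age (waz) and head-circumference (headcz) Z-scores as outputs.
- **Tables 14.3.4.1 to 14.3.4.4:** add waz to the weight tables and haz to the height tables, each with change from baseline by visit and, in the by-age tables, by age band fixed at baseline so that children do not move between bands over follow-up.
- **Tables 14.3.7.1 to 14.3.7.2:** add headcz and its change wherever the reference returns a value, with the number of children contributing. The reference data are not in the documents, so the ages covered cannot be stated here.
- **Raw summaries:** keep them as description.
- **Table 14.3.5.6:** keep it, and state that conclusions about open-label BMI change rest on the BMI Z-score analysis in Table 14.3.5.10, because raw BMI can change with age alone.

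The cost is SAP wording, three input variables that are already collected and a few table columns. The downside is dependence on a single reference population, which the BMI Z-score already accepts.

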12.6 Tanner Assessment of Pubertal Development

The Tanner scale will be used to assess and stage physical development in subjects ≥ 8 years of age. For subjects ≤ 5 years of age, only height and head circumference will be used to stage development. Between the age of 5 and 8 the subjects' physical development will be determined using the BMI.

Two measures are collected for males (genital development (5 stages G1–G5) and pubic hair (6 stages PH1–PH6)) and females (breast development (5 stages B1–B5), pubic hair (6 stages PH1–PH6)) respectively.

Tanner scores for pubertal assessment in subjects ≥ 8 years of age during the study will be analyzed using the web application (<http://vps.stefvanbuuren.nl/puberty>). The Tanner scores for each measure will be uploaded to the website as a .csv file. The file will contain the subject's sex and age in months to two decimal places. An example file is available to ensure the correct format for uploading the file to the site. This tool will calculate SD scores of individual observations of Tanner scores for each assessment.

Results from the Tanner assessment will be tabulated for each measure by scheduled visit.

For subjects ≥ 8 years of age the SD score and change from baseline in the SD score for each pubertal assessment will be listed and summarized descriptively by scheduled visit.

The result, change from baseline and % change from baseline for head circumference will be listed and summarized descriptively by scheduled visit. Descriptive statistics will also be presented for the following age group: 2 to ≤ 5 years, > 5 to < 8 years and ≥ 8 years.

12.7 Epilepsy

Number and type of epilepsy seizures in children diagnosed with epilepsy will be tabulated, using the Epilepsy Seizures Diaries that are completed by parents at the time of the seizures. For the number of epilepsy seizures, percentages will be based on the number of children diagnosed with epilepsy.

The median number of epilepsy seizures will be summarized by scheduled visit and across all visits. At each visit Wilcoxon rank-sum test will be performed to compare the number of seizures occurring between the two groups.

Example SAS code for this analysis is given below:

```
proc NPAR1WAY data=epil wilcoxon;  
  class trtp;  
  var numepil;  
  exact wilcoxon;  
run;
```

